4.2 SAFETY ANALYSIS SET

There are no safety endpoints in this study.

4.3 OTHER ANALYSIS SET

Not applicable

4.4 SUBGROUPS

No subgroup analysis will be performed. However, the vaccine effectiveness will be assessed using several different time points as described in Section 7 (refer to Section 7.2.3.5.1).

5 ENDPOINTS AND COVARIATES

5.1 EFFICACY/EFFECTIVENESS ENDPOINT(S)

5.1.1 Primary Endpoint

• VE calculated as 1 minus the hazard ratio for gonococcal infection between the recipients of both Trumenba (at least one dose) and MenACWY (at least one

PFIZER CONFIDENTIAL

CT24-WI-GL03-RF03 2.0 Non-Interventional Statistical Analysis Plan For Secondary Data Collection Study 01-Jun-2020 Page 8 of 28 dose) vaccines and the reciepients of MenACWY vaccine only multiplied by 100, adjusted for age, sex, and US region.

In this analysis, the cases are those who have at least one diagnosis code for gonococcal infection (Appendix Table 1) during follow-up. Each individual will be followed for the outcome from 14 days after their zero time until the end of the follow-up period, censoring the follow-up at death date (if known) or plan disenrollment (if known).

5.2 SAFETY ENDPOINT(S)

No safety endpoints in this study

5.3 OTHER ENDPOINTS

5.3.1 Secondary Endpoint(s)

 VE calculated as 1 minus the hazard ratio for gonococcal infection between the recipients (aged 15-30 years) of both Trumenba (at least two doses) and MenACWY (at least one dose) vaccines and the recipients (aged 15-30 years) of MenACWY vaccine only multiplied by 100, adjusted for (age, sex, and US region, as appropriate).

In this analysis, the cases are those who had at least one diagnosis code of gonococcal infection during follow-up. Each individual will be followed for the outcome from 14 days after their zero time until the end of the follow-up period, censoring the follow-up at death date (if known) or plan disenrollment (if known).

 VE calculated as 1 minus the hazard ratio for chlamydial infection between the recipients (aged 15-30 years) of both Trumenba (at least one dose) and MenACWY (at least one dose) vaccines and the recipients (aged 15-30 years) of

PFIZER CONFIDENTIAL

CT24-WI-GL03-RF03 2.0 Non-Interventional Statistical Analysis Plan For Secondary Data Collection Study 01-Jun-2020 Page 9 of 28 MenACWY vaccine only multiplied by 100, adjusted for (age, sex, and US region).

In this analysis, the cases are those who had at least one claim of chlamydial infection in the database. Each individual will be followed for the outcome from 14 days after their zero time until the end of the follow-up period, censoring the follow-up at death date (if known) or plan disenrollment (if known).

3. VE calculated as 1 minus the hazard ratio for chlamydial infection between the recipients (aged 15-30 years) of both Trumenba (at least two doses) and MenACWY (at least one dose) vaccines and the reciepients (aged 15-30 years) of MenACWY vaccine only multiplied by 100, adjusted for age, sex, US region.

In this analysis, the cases are those who had at least one claim of chlamydial infection in the database. Each individual will be followed for the outcome from 14 days after their zero time until the end of the follow-up period, censoring the follow-up at death date (if known) or plan disenrollment (if known).

5.3.2 Exploratory Endpoints

 VE calculated as 1 minus the hazard ratio for gonococcal infection between the recipients (aged 16-23 years) of both Trumenba (at least one dose) and MenACWY (at least one dose) vaccines and the recipients (aged 16-23 years) of MenACWY vaccine only multiplied by 100, adjusted for potentially confounding variables (age, sex, and US region, as appropriate).

In this analysis, the cases are those who had at least one claim of gonococcal infection in the database. Each individual will be followed until the end of the follow-up period, censoring the follow-up at death date (if known) or plan disenrollment (if known).

PFIZER CONFIDENTIAL

CT24-WI-GL03-RF03 2.0 Non-Interventional Statistical Analysis Plan For Secondary Data Collection Study 01-Jun-2020 Page 10 of 28 2. VE calculated as 1 minus the hazard ratio for gonococcal infection between the recipients (aged 15-30 years) of both Trumenba (at least one dose) and MenACWY (at least one dose) vaccines and the recipients (aged 15-30 years) of MenACWY vaccine only multiplied by 100, adjusted for potentially confounding variables (age,sex, and US region).

In this analysis, the cases are those who had at least one claim of gonococcal infection in the database. Each individual will be followed for the outcome from 14 days after their zero time until the end of the follow-up period, censoring the follow-up at death date (if known) or plan disenrollment (if known).

The analysis will be carried out by different periods of study (zero time to 12 months post zero time, zero time to 24 months post zero time, zero time to 36 months post zero time, and zero time to 48 months post zero time)

Variable	Role	Operational definition
Age (years)	Baseline characteristic and potential confounder	Age will be calculated based on the 1 st date of Trumenba vaccination for the exposed cohort and the date of the 1 st dose of MenACWY for the unexposed cohort
Sex	Baseline characteristic and potential confounder	Sex will be categorized as female and male
US region	Baseline characteristic and potential confounder	US region which is categorized as : E=Northeast S=South MW=Midwest W=West

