9.3. Variables

In this study, the variables of interest are age, gender, state of residence, date of vaccination and the date of disease diagnosis.

PFIZER CONFIDENTIAL CT24-WI-GL02-RF02 4.0 Non-Interventional Study Protocol Template For Secondary Data Collection Study 01-Jun-2022 Page 12 of 22

Table 1.Variable List

Variable	Role	Operational Definition
Birth Year	Covariate	Birth year (age to be calculated based on July 1 of birth year)
Gender	Covariate	Male, Female, Unknown
Residence (ZIP code)	Covariate	First 3 digits of the zip code from individuals' most recent enrollment
MenACWY vaccination	Non-exposure	Current procedural terminology (CPT) codes and National Drug Codes (NDC) listed below
Trumemba vaccination	Exposure	CPT and NDCs listed below
Gonococcal infection	Primary Outcome	ICD-10-CM codes listed below
Chlamydial infection	Reference disease Outcome	ICD-10-CM codes listed below

Code	Туре
A540	ICD-10-CM
A5400	ICD-10-CM
A5401	ICD-10-CM
A5402	ICD-10-CM
A5403	ICD-10-CM
A5409	ICD-10-CM
A541	ICD-10-CM
A542	ICD-10-CM
A5421	ICD-10-CM
A5422	ICD-10-CM
A5423	ICD-10-CM
A5424	ICD-10-CM
A5429	ICD-10-CM
A543	ICD-10-CM
A5430	ICD-10-CM
A5431	ICD-10-CM
A5432	ICD-10-CM
A5433	ICD-10-CM
A5439	ICD-10-CM
A544	ICD-10-CM
A5440	ICD-10-CM
A5441	ICD-10-CM
A5442	ICD-10-CM
A5443	ICD-10-CM
A5449	ICD-10-CM
A545	ICD-10-CM
A546	ICD-10-CM
A548	ICD-10-CM
A5481	ICD-10-CM
A5482	ICD-10-CM
A5483	ICD-10-CM
A5484	ICD-10-CM
A5485	ICD-10-CM
A5486	ICD-10-CM
A5489	ICD-10-CM
A549	ICD-10-CM

Table 2. Diagnosis Codes for Identifying Gonococcal Infections

Code	Туре
A55	ICD-10-CM
A560	ICD-10-CM
A5600	ICD-10-CM
A5601	ICD-10-CM
A5602	ICD-10-CM
A5609	ICD-10-CM
A561	ICD-10-CM
A5611	ICD-10-CM
A5619	ICD-10-CM
A562	ICD-10-CM
A563	ICD-10-CM
A564	ICD-10-CM
A568	ICD-10-CM
A71	ICD-10-CM
A710	ICD-10-CM
A711	ICD-10-CM
A719	ICD-10-CM
A74	ICD-10-CM
A740	ICD-10-CM
A748	ICD-10-CM
A7481	ICD-10-CM
A7489	ICD-10-CM
A749	ICD-10-CM

 Table 3.
 Diagnosis Codes for Identifying Chlamydial Infections

Code	Туре	Description
90734	CPT	Menactra/Menveo Vaccination
90619	CPT	Menquadfi Vaccine
49281-0589-05	NDC	Menactra Vaccine
46028-0208-01	NDC	Menveo Vaccine
58160-0955-09	NDC	Menveo Vaccine
49281-0589-58	NDC	Menactra Vaccine
49281-0590-58	NDC	Menquadfi Vaccine
46028-0218-11	NDC	Menveo Vaccine
58160-0958-01	NDC	Menveo Vaccine
58160-0959-01	NDC	Menveo Vaccine
46028-0219-11	NDC	Menveo Vaccine
54569-5687-01	NDC	Menactra Vaccine
50090-1890-01	NDC	Menactra Vaccine
49281-0590-05	NDC	Menquadfi Vaccine

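### The SAP adjusts the primary VE for US region only, although the protocol lists state and 3-digit ZIP, so any within-region link between gonorrhoea rate and Trumenba uptake would stay in the estimate

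*SAP*

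**What the plan says.** Protocol 9.3 states that "the variables of interest are age, gender, state of residence, date of vaccination and the date of disease diagnosis". Table 1 in the same section has a residence row with the role of covariate, defined as "First 3 digits of the zip code" at the most recent enrollment. Protocol 9.7 then specifies covariate-adjusted Cox models without naming the covariates.

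SAP 5.1.1 defines the primary VE as "adjusted for age, sex, and US region". The SAP covariate table (5.3.2 and 5.4) has one geographic row, "US region which is categorized as" "E=Northeast S=South MW=Midwest W=West", and a fifth level, Unknown, follows on the next page. State and ZIP do not appear in the SAP.

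Two SAP provisions could weaken geographic control further. Section 7.2.1 makes adjustment for the three covariates conditional on its being appropriate. Section 7.2.1.1 removes from the multivariable model any covariate that fails proportionality and refers it to a stratified analysis.

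**The concern.** A hazard ratio adjusted for region and one adjusted for state are different estimates. The protocol lists the finer variables and the SAP uses the coarsest, without a derivation or a reason.

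The primary model has only three covariates, and residual confounding is the first limitation named in protocol 9.9. A region pools areas that may differ in gonorrhoea incidence and in Trumenba uptake. If the two are associated inside regions, part of that association is read as vaccine effect, or as lack of it. The chlamydia analyses use the same region term, so they carry the same gap.

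**Working it through.** **The plan's own figure.** SAP section 3 gives 500,000 people, 15% exposed, event probabilities 0.0036 and 0.0048, HR 0.80, two-sided alpha 0.05 and power 94%.

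- Events: m = 75,000 × 0.0036 + 425,000 × 0.0048 = 270 + 2,040 = 2,310.
- Exposure ratio: k = 75,000/425,000 = 0.1765.
- Power = Φ(√(k·m) × |HR − 1|/(k·HR + 1) − 1.96) = Φ(20.19 × 0.2/1.141 − 1.96) = Φ(1.58) = 0.943.

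The 94% reproduces. It contains no geographic term, so it does not bear on the covariate choice.

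**Scale.** The SE of the log HR is about 1/√(2,310 × 0.15 × 0.85) = 0.058. At HR 0.80 the 95% CI is about 0.71 to 0.90, or VE 10% to 29%.

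**Two areas in one region (assumed values).** Take equal-sized areas with mean uptake 15%, rate ratio R between them, and uptake uH in the high-rate area and uL in the low-rate area. The factor left on the HR after region adjustment is

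B = [(uH·R + uL)/(uH + uL)] ÷ [((1−uH)·R + (1−uL))/((1−uH) + (1−uL))].

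For R = 2, uH = 10%, uL = 20%: B = (0.40/0.30)/(2.60/1.70) = 1.333/1.529 = 0.872. A true VE of 20% then shows as 1 − 0.8 × 0.872 = 30.3%.

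| R | Uptakes | VE shown, lower uptake in high-rate area | VE shown, reversed |
|---|---|---|---|
| 1.5 | 12% and 18% | 23.7% | 16.2% |
| 2 | 10% and 20% | 30.3% | 9.3% |
| 3 | 10% and 20% | 35.2% | 3.8% |

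If rate or uptake is uniform within the region, B = 1 and nothing is left over.

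**Fifty states in four regions.** N, exposed share and reference risk come from SAP section 3, with true HR 0.80. The number of equal-sized states, the within-region SDs and the correlation are assumptions. There were 300 draws per scenario. For each draw the rare-event stratified Cox score equation was solved for h = HR:

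Σ over strata of [D1 − D × n1·h/(n1·h + n0)] = 0,

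where D1 is exposed events, D is all events, and n1 and n0 are exposed and reference persons in the stratum. Strata were first regions, then states. Where a range is shown, it covers repeat runs with different random draws.

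| SD log rate | SD logit uptake | Correlation | Mean region-adjusted VE | Bias in SEs |
|---|---|---|---|---|
| 0.2 | 0.3 | +0.3 | about 19% | about 0.2 |
| 0.3 | 0.5 | +0.5 | 14.4% to 15.1% | 1.0 to 1.1 |
| 0.4 | 0.5 | +0.5 | about 13% | 1.4 |
| 0.2 | 0.3 | -0.3 | about 21% | about 0.2 |
| 0.4 | 0.5 | -0.5 | 26.3% to 26.7% | about 1.3 |
| 0.3 | 0.5 | +0.1 | 18.7% to 18.9% | about 0.3 |
| 0.3 | 0.5 | 0 | about 20% | nil on average |

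In the last row, 90% of single draws still ran from about 17.4% to 22.6%, and one study sees one draw. State strata returned 20.0% throughout, with an SE increase of up to about 1.5% (for example 0.0614 to 0.0622, or 1.3%).

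**Feasibility.** With 50 states, 2,310/50 = 46 events and 270/50 = 5 exposed events per stratum. With an assumed 500 to 900 ZIP3 areas, it is 4.6 down to 2.6 events and about 0.5 down to 0.3 exposed events per area. That is too sparse for ZIP3 fixed effects.

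**The case against.** **Region may simply be a roll-up.** Protocol Table 1 also lists birth year as a covariate, from which age is calculated. ZIP3 can be read in the same way, as a source field. Protocol 9.7 never specifies a state- or ZIP-adjusted model, and 9.3 leaves further detail to the SAP. This stands: a reader might infer three incompatible definitions, but the levels are nested. What is missing is the derivation and the reason for coarsening.

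**No breach is shown.** Both documents let the SAP modify the protocol and reserve an amendment for major changes to the primary endpoint or its analysis. Nothing shows that a coarser geographic level is major, so the absence of an amendment proves nothing.

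**Harm is not shown.** Bias needs rate and uptake both to vary within regions and to be associated. The documents give neither by state. A reader might infer that the primary VE is biased, or biased in a known direction; the documents do not support that.

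**State strata recover 20.0% by construction.** The calculation puts all confounding between states and records state without error. Table 1 takes residence at the most recent enrollment, not at zero time, in young people followed for up to about seven years. Randomly misassigning the state of 20% of people (an assumption) gives 18.0% in the scenario with SDs 0.3 and 0.5 and correlation +0.5. That is better than region, but not 20%.

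**Chlamydia is a check.** Protocol 9.9 plans it as a reference outcome, and geographic confounding that inflates VE could show there. It can signal the problem but cannot remove it, and the rule covers only an HR below 1.0.

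**Conclusion.** The point holds as a conditional weakness with a cheap remedy. The SAP adjusts for the coarsest of three nested levels without saying how or why, and any within-region association between gonorrhoea rate and Trumenba uptake would pass into the primary VE.

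The size depends wholly on assumed variation between states. At correlations of 0.3 to 0.5 in either direction, a true VE of 20% moves on average by about 1 to 7 points, or roughly 0.2 to 1.4 SE. At +0.1 it moves by about 1 point, and at zero by nothing on average. The larger shifts in the two-area table only show how the mechanism works. The case for change rests on the small cost of finer control in a model with three covariates, not on evidence that the estimate is wrong.

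**What to change.** In SAP 5.1.1, 5.4 and 7.2.1.1:

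- Derive state of residence from the state field or the 3-digit ZIP, using the enrollment record at or nearest zero time where available. State the derivation.
- Stratify the adjusted Cox model on state for the primary, secondary and exploratory endpoints. Each state then has its own baseline hazard, so the rule that drops non-proportional covariates no longer threatens geographic control.
- Make Unknown its own stratum, or exclude it under the rule on missing demographic data. Say which.
- Report the region-adjusted model alongside as a sensitivity analysis, and keep region for description in Tables 1.1 and 1.2.
- Align protocol 9.3 and its Table 1 with the variable chosen.

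The cost is SAP wording, one lookup from ZIP to state, one strata term and an SE increase of up to about 1.5%. States with events in only one cohort would add little information. Confounding below state level, or from misrecorded residence, would remain.

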5.4 COVARIATES

PFIZER CONFIDENTIAL

CT24-WI-GL03-RF03 2.0 Non-Interventional Statistical Analysis Plan For Secondary Data Collection Study 01-Jun-2020 Page 11 of 28

Variable	Role	Operational definition
		O=Unknown

6 HANDLING OF MISSING VALUES

Analyses will be based on all available data. Participants who have data missing for a certain analysis will be excluded only from that analysis. No imputation for missing values will be performed.

7 STATISTICAL METHODOLOGY AND STATISTICAL ANALYSES

7.1 STATISTICAL METHODS

Means, medians, and standard deviations will be provided for continuous variables when performing descriptive analysis of continuous data. Numbers and percentages will be provided for dichotomous and polychotomous variables when performing descriptive analysis of categorical data. Bivariate comparisons of baseline characteristics and outcomes measures will be provided. Appropriate tests (e.g., t-test, chi-square test) will be used based on the distribution of the measure. The cumulative incidence rate for clinical outcomes will be calculated. The incidence rate will be calculated as the number of patients who experience the event divided by the observed time at risk. An unadjusted Kaplan Meier curve will be drawn to illustrate time-to-event.

7.2 STATISTICAL ANALYSES

7.2.1 Primary Endpoint - Effectiveness of trumenba against gonococcal infection.

The primary endpoint is the vaccine effectiveness (VE), to be calculated as 1 minus the hazard ratio for gonococcal infection between the recipients of both Trumenba (at least one dose) and MenACWY (at least one dose) vaccines and the recipients of MenACWY vaccine only multiplied by 100, adjusted for potentially confounding variables (age, sex and US region, as appropriate).

7.2.1.1 Primary Endpoint - Main Analysis

Vaccination Status

If a participant received at least one dose of Trumenba and at least one dose of MenACWY vaccine will be considered as vaccinated (exposed population).

Analysis

We will assess gonococcal infection that occurred between 14 days after zero time and till end of the study period. We will censor the data at death date (if known), plan disenrollment, or the end of the study period, whichever comes first. In descriptive analyses, we will fit Kaplan-Meier curves. We will also create unadjusted and covariate adjusted Cox proportional hazard regression models with time varying approach verifying first that the proportionality assumption was satisfied for all independent variables. Since the individuals entered into the surveillance at different points of time, we will employ the computing process algorithm of the proportional hazard model where the date of entry and the date of end of follow-up will be used in the model instead of time contribution to compute the hazard ratios.

Hazard ratios (HRs) will be estimated by exponentiation of the coefficient for the vaccine variable in these models, with vaccine effectiveness estimated as $(1-HR)\times100\%$. Standard errors (SEs) for the coefficients will be used to estimate p-values and 95% CIs for the HRs. If a covariate does not satisfy the assumption of proportionality, we will exclude the variable for the multivariable model and will perform the stratified analysis using the covariate. Both crude and adjusted VE with its corresponding 95% CI will be calculated.

7.2.1.2 Primary Endpoint – Sensitivity Analysis

In a sensitivity analysis, we will exclude coinfection cases, i.e., individuals with diagnosis codes for gonorrhea and chlamydia within 30 days of one another. Although the case definition will differ from the main analysis, the method of evaluation will be same as the main analysis.

7.3 SAFETY ENDPOINTS

Not applicable

7.4 OTHER ENDPOINTS

7.4.1 Safety Analyses

Not Applicable

7.4.2 Analyses of other endpoints

7.4.2.1 Secondary Endpoint 1 - Effectiveness of trumenba against gonococcal infection.

VE calculated as 1 minus the hazard ratio for gonococcal infection between the recipients (aged 15-30 years) of both Trumenba (at least two doses) and MenACWY (at least one dose) vaccines and the recipients (aged 15-30 years) of MenACWY vaccine only multiplied by 100, adjusted for potentially confounding variables.

7.4.2.1.1 Secondary Endpoint 1 - Main Analysis

Vaccination Status

If a participant received at least two doses of Trumenba and at least one dose of MenACWY vaccine will be considered as vaccinated (exposed population).

Analysis

We will assess gonococcal infection that occurred between 14 days after zero time and till end of the study period. The analysis will be performed as written in the Section 7.2.1.1.

7.4.2.2 Secondary Endpoint 2 - Effectiveness of trumenba against chlamydial infection

VE calculated as 1 minus the hazard ratio for chlamydial infection between the recipients (aged 15-30 years) of both Trumenba (at least one dose) and MenACWY (at least one dose) vaccines and the recipients (aged 15-30 years) of MenACWY vaccine only multiplied by 100, adjusted for potentially confounding variables.

PFIZER CONFIDENTIAL CT24-WI-GL03-RF03 2.0 Non-Interventional Statistical Analysis Plan For Secondary Data Collection Study 01-Jun-2020 Page 14 of 28

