8.1.2. Secondary Objectives

- 1. To examine the effect of at least 2 doses of Trumenba on gonococcal infection in adolescents and young adults of 15-30 years in the US.
- 2. To examine the effect of at least 1 dose of Trumenba on chlamydial infection in adolescents and young adults of 15-30 years in the US.
- 3. To examine the effect of at least 2 doses of Trumenba on chlamydial infection in adolescents and young adults of 15-30 years in the US.

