9.9. Strengths and Limitations of the Research Methods

Strengths

A significant strength of observational retrospective analyses is that they provide a better understanding of the study population in real world clinical practice as compared to the controlled conditions of a clinical trial.

Limitations

There are several limitations in this study. Given that this is an observational study using health care administrative claims data, residual confounding due to missing or unmeasured information is possible. To examine this, we will assess the effect of meningococcal vaccination on another sexually transmitted disease occuring, at the same age group, as reference disease outcome. If the HRs in any of these models are less than 1.0, it would indicate that residual confounding exists and may result in adjustment of our vaccine effectiveness (VE) estimates.

Second, health care administrative claims data will be available from 01 January 2016 through 31 December 2022. It is possible that some participants may have received a Trumenba vaccination prior to January 1, 2016 or during a period in which we do not have their claims data and be misclassified as unvaccinated with Trumenba. This may underestimate Trumenba vaccine effectiveness because the Men-ACWY-only cohort will include Trumenba vaccinated patients.

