7.4.2.2.1. Secondary Endpoint 2 - Main Analysis

Vaccination Status

If a participant received at least one dose of Trumenba and at least one dose of MenACWY vaccine will be considered as vaccinated (exposed population).

Analysis

We will assess chlamydial infection that occurred between 14 days after zero time and till end of the study period. The analysis will be performed same as in Section 7.2.1.1.

7.4.2.3 Secondary Endpoint 3 - Effectiveness of Trumenba against chlamydial infection.

VE calculated as 1 minus the hazard ratio for chlamydial infection between the recipients (aged 15-30 years) of both Trumenba (at least one dose) and MenACWY (at least one dose) vaccines and the recipients (aged 15-30 years) of MenACWY vaccine only multiplied by 100 adjusted for potentially confounding variables.

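### The protocol uses chlamydia as a reference outcome to reveal residual confounding; the SAP reports the same hazard ratio as Trumenba effectiveness and does not carry that use over

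*SAP*

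**What the plan says.** **Protocol.** Table 1 in section 9.3 lists gonococcal infection as the primary outcome and chlamydial infection as "Reference disease Outcome". Section 9.9 gives the purpose. Because unmeasured confounding is possible in claims data, "we will assess the effect of meningococcal vaccination on another sexually transmitted disease occuring, at the same age group, as reference disease outcome". It then states how the result is to be read: "If the HRs in any of these models are less than 1.0, it would indicate that residual confounding exists and may result in adjustment" of the VE estimates.

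Section 8.1.2 also lists chlamydia under secondary objectives 2 and 3. Objective 2 reads "To examine the effect of at least 1 dose of Trumenba on chlamydial infection in adolescents and young adults of 15-30 years", and objective 3 is the same for at least two doses. Neither mentions the reference role.

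**SAP.** Sections 7.4.2.2 and 7.4.2.3 are headed "Secondary Endpoint 2 - Effectiveness of trumenba against chlamydial infection" and "Secondary Endpoint 3 - Effectiveness of Trumenba against chlamydial infection". Section 5.3.1, items 2 and 3, defines the measure as "VE calculated as 1 minus the hazard ratio for chlamydial infection between" the two cohorts, multiplied by 100. Sections 7.4.2.2.1 and 7.4.2.3.1 apply the primary analysis of 7.2.1.1 unchanged. Table shells 2.1, 3.1 and 3.2, all titled as effectiveness of Trumenba, have unadjusted and adjusted VE rows for chlamydia. The word reference is used in the SAP only for the MenACWY-only cohort.

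**The concern.** A reference outcome and an effectiveness endpoint are read in opposite ways. For a reference outcome the expected HR is 1, and a departure below 1 casts doubt on the primary result. For an effectiveness endpoint an HR below 1 is a favourable finding. The protocol takes the first view in Table 1 and 9.9. The SAP, which supplies the detailed methodology, takes the second throughout.

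The primary VE is adjusted only for age, sex and US region (SAP 5.1.1). Sexual behaviour, testing frequency and health seeking are not among the covariates. If Trumenba recipients differ from MenACWY-only recipients in these respects, gonococcal and chlamydial HRs could both fall below 1 without any vaccine effect. The comparison in 9.9 is meant to reveal that pattern. An analyst who follows the SAP exactly would label it as effectiveness against a second infection, with no instruction to bring it to bear on the gonococcal estimate. Any later adjustment under 9.9 would have to be devised after the results were known.

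**Working it through.** Neither document gives an expected HR, power or event count for chlamydia, so there is no planned figure to reproduce. The check compares the text and then applies each document's rule to the same number.

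**Step 1: the documents side by side.**

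| | Protocol | SAP |
|---|---|---|
| Role of chlamydia | Reference disease outcome (Table 1, 9.9); neutral effect wording in 8.1.2 | Effectiveness endpoint (5.3.1 items 2–3, 7.4.2.2, 7.4.2.3) |
| Meaning of HR < 1 | Residual confounding (9.9) | Positive VE (5.3.1, 7.2.1.1) |
| Consequence for gonococcal VE | May be adjusted (9.9) | None stated |
| Method linking the two HRs | None stated | None stated |

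The coinfection sensitivity analysis in SAP 7.2.1.2 does not fill the gap: it changes the case definition and does not compare the two HRs. The footnotes under the VE shells define VE by the gonococcal HR only, although chlamydia rows stand above them.

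**Step 2: one HR, two readings.** Under the SAP, VE = (1 − HR) × 100. A chlamydia HR of 0.90 gives (1 − 0.90) × 100 = 10%, and 0.85 gives 15%. Under protocol 9.9 both values indicate residual confounding.

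**Step 3: illustration of what depends on the reading.** Inputs:
- Gonococcal HR 0.80, the 20% VE on which protocol 9.5 and SAP section 3 base their calculations.
- Chlamydia HR from 0.80 to 0.95. This is an assumption; the documents give no value.
- Confounding multiplies both HRs by the same factor *c*, and Trumenba has no effect on chlamydia. Both are assumptions.

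Then observed chlamydia HR = *c*, and observed gonococcal HR = (true gonococcal HR) × *c*. It follows that

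true gonococcal HR = observed gonococcal HR / observed chlamydia HR.

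| Chlamydia HR | Chlamydia VE as the SAP prints it | Ratio of HRs | Gonococcal VE from the ratio |
|---|---|---|---|
| 0.95 | 5% | 0.80/0.95 = 0.842 | 15.8% |
| 0.90 | 10% | 0.80/0.90 = 0.889 | 11.1% |
| 0.85 | 15% | 0.80/0.85 = 0.941 | 5.9% |
| 0.80 | 20% | 0.80/0.80 = 1.000 | 0% |

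In every row the SAP as written reports a gonococcal VE of 20%.

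**The case against.** The SAP tests no hypothesis (sections 3 and 3.1), so it draws no formal conclusion about chlamydia that could contradict the protocol. VE is a simple transform of the HR, and a reader can recover one from the other. The chlamydia estimate uses the same model as the primary analysis and appears in the same tables. Nothing in the SAP withdraws 9.9, so the protocol's interpretation could still be applied when the report is written, and 9.9 says only that adjustment may follow. The MenACWY-only comparator was also chosen to limit differences in health seeking and risk behaviour (protocol 9.1).

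Most of this stands, and it limits the point. A reader might infer that the study loses its only protection against unmeasured confounding. The documents do not support that: the comparator is a design control, and the chlamydia HR will be available. A reader might also infer that a claim of effectiveness against chlamydia will be made. Neither document says so. Nor is the conflict purely between protocol and SAP, since the objectives in 8.1.2 are worded for chlamydia just as they are for gonorrhoea.

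What the objection does not answer is that the document governing the analysis gives the estimate a label, a measure and table titles that point the opposite way from 9.9, and gives no instruction for using it as 9.9 intends. A comparator chosen to reduce confounding is also different from a diagnostic of whether it did.

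**Conclusion.** The point holds as a conflict of role and interpretation. Protocol Table 1 and 9.9 read a chlamydia HR below 1.0 as residual confounding; the SAP defines and tabulates it as Trumenba effectiveness and omits the confounding reading. The opposite readings come from headings, definitions and table shells, not from opposing decision rules.

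The size cannot be fixed from the documents. In the illustration, a chlamydia HR of 0.85 or 0.90 moves a gonococcal VE of 20% to about 6% or 11%. This rests on a gonococcal HR of 0.80, equal confounding on both outcomes and no effect of Trumenba on chlamydia. The documents establish none of these; the last is implied by the rule in 9.9 but not stated. A reader might take the 6% as the share truly due to the vaccine. It is not an estimate of that, and the ratio is suited to stand beside the primary VE, not to replace it. The change is worth making because it is cheap and settles beforehand how a result bearing on the primary estimate will be read.

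**What to change.** 1. In SAP 5.3.1 (items 2–3), 7.4.2.2, 7.4.2.3 and Tables 2.1, 3.1 and 3.2, name chlamydia as the reference (negative-control) outcome. Report its HR with a 95% CI, and state that no effectiveness claim will be made from it.
2. Add a supplementary row beside the primary VE giving the ratio of the gonococcal HR to the chlamydia HR. Both HRs come from the same people, so take the CI from a joint model or a bootstrap. State the equal-confounding assumption next to the row.
3. Align objectives 2 and 3 in protocol 8.1.2 with the reference role.
4. If the sponsor does intend chlamydia as an effectiveness endpoint, change protocol 9.9 and Table 1 instead, and name another reference outcome.

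The ratio is one workable method; 9.9 prescribes none. The cost is wording in both documents and one further estimate from data already in the analysis. The downside for the sponsor is giving up chlamydia VE as a finding.
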